**Figure 3: Monthly Study Accrual Rates**

### Specific Aim 1:

#### Primary outcome:

To determine *overall* colonization status in children presenting with *S. aureus* abscesses who do and do not receive systemic antibiotic therapy at two time points (baseline and 1 month); a hierarchical logistic regression model will be used with colonization status as the outcome. Follow-up tests will be utilized when necessary.

#### Secondary outcomes:

1. To determine colonization status *at each body site* (nose, axilla and inguinal folds) independently in children presenting with *S. aureus* abscesses who do and do not receive systemic antibiotic therapy at two time points (baseline and 1 month); a hierarchical logistic regression model will be used with colonization status as the outcome at each body site.
2. A chi-squared test of independence will be used to determine if there is an association between colonization (determined at baseline) and presence of abscess at 1 month.

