**APPROACH/PRELIMINARY DATA**

**Risk factors for *S. aureus* SSTI**

MRSA colonization confers risk for SSTI: A prevalence study of *S. aureus* nasal colonization in the St. Louis pediatric population was performed by Fritz et al.; 1300 children ages birth to 18 years were enrolled. The rates of MRSA and MSSA nasal colonization were 2.5% and 25.5%, respectively [10]. To investigate the relationship between *S. aureus* nasal colonization and subsequent SSTI, the 1300 children enrolled in the above prevalence study were followed for one year, during which the overall incidence of SSTI was 13%. Baseline MRSA colonization conferred risk for subsequent SSTI (OR 4.6, 95% CI 1.8, 11.9) [10]. Another study performed by Kaplan et al showed that multiple *S. aureus* colonization sites were related with higher recurrence rates [26].

Household member with SSTI: *S. aureus* SSTI cluster in households. In a study performed by Fritz et al, SSTI in a household contact was associated with increased risk of SSTI in the index patient (Figure 1) [22].

Colonization pressure is a Risk Factor for subsequent SSTI: Colonization pressure (CP) is a measure used in healthcare settings to determine the magnitude of the microorganism reservoir. MRSA CP has been shown to predict infections in hospitals [34]. During my fellowship at Washington University under the mentorship of [name], MSCI, I participated in a study aimed to apply the concept of CP to the community setting by evaluating whether the proportion of colonized household contacts increased the prevalence of persistent colonization or the incidence of recurrent infections in index patients with baseline SSTI. We demonstrated that high MRSA CP in households was associated with persistent MRSA colonization in pediatric patients. We found a relationship between *S. aureus* household CP and a history of SSTI in household contacts in the year prior [35].

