### Specific Aim 2:

#### *Primary outcome:*

To measure incidence of SA recurrent skin and soft tissue infections at 3 months in patients who did or did not receive systemic antibiotic therapy. A binary logistic regression will be performed to see if antibiotic therapy is associated with SSTI at 3 months after adjusting for covariates.

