#### *Secondary outcomes:*

1. To measure incidence of SA recurrent skin and soft tissue infections at 1, 6 and 12 months independently in patients who did and did not receive systemic antibiotic therapy. Separate logistic regressions will be performed (at each time point) to see if antibiotic therapy is associated with SSTI after adjusting for covariates.
2. In order to assess the trend of SSTI's over 1 year follow-up we will use the Cochran-Armitage test for trend to determine if there are more SSTI's in the following year for patients colonized (determined at baseline).

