### Potential limitations:

Recruitment success rate is estimated to be around 30% in order to collect the desired patient sample (50 patients) in a 1 year period; this is based on a prior study in which the same population was targeted [39]. We recognize the complexity of having patients come to clinic for research purposes only in follow up. SIU School of Medicine's Department of Pediatrics is providing funds to complete the study beyond the 12 month period. Patient reimbursement of a \$20 check will be given at the follow-up visit for study purposes, without any charges to medical insurance. In previous studies conducted by our team, we had had a high longitudinal retention rate when the same incentive was given [39, 40]. Specimens will be obtained by research personnel and the collection technique. The surface area swabbed and the pressure used will be standardized for all participants. We have validated the shipping procedures for specimen transport to our collaborators at Washington University. We would like to evaluate whether shipment of the swabs can be done in a timely manner and whether the length of time required for shipment impacts the ability to successfully recover microorganisms. Reaching participant for follow-up phone calls may be a challenge, especially at 6 and 12 months after study enrollment; thus, we will obtain multiple methods of contact for each participant. A source of bias that we will have is the variability in the treating physician's decision to administer antibiotics or not. Adjusting for possible confounding factors and covariates will be made but these factors will not play a role in the primary outcome which is *S. aureus* colonization.

**Conclusion:** The Research Seed Grant, RSG, is an important step in achieving my career goal of becoming an independent investigator at SIU and will offer me a tremendous opportunity to help our patient population. The goal of this project is to obtain preliminary data which will allow me to apply for future external funding to be able to recruit more patients and to show a statistical significance. Recurrent *S. aureus* SSTI have become a major source of morbidity in our pediatric population. Decreasing the number of recurrent SSTI will decrease ED and PCP clinic visits and will benefit our public health.

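### The two colonization-to-SSTI tests are crude and pool treated with untreated children, so they describe an association but cannot show colonization to be an independent risk factor

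*Combined protocol and SAP*

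**What the plan says.** Two analyses take colonization at enrollment as the exposure and later infection as the outcome.

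- Specific Aim 1, Secondary outcomes, item 2: a chi-squared test for an "association between colonization (determined at baseline) and presence of abscess at 1 month".
- Specific Aim 2, Secondary outcomes, item 2: a Cochran-Armitage trend test to "determine if there are more SSTI's in the following year for patients colonized (determined at baseline".

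Neither item lists a covariate, a stratum or the antibiotic group, so as written each runs on all children together.

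The analyses with antibiotics as the exposure are handled differently. The Specific Aim 2 primary outcome reads: "A binary logistic regression will be performed to see if antibiotic therapy is associated with SSTI at 3 months after adjusting for covariates". The models at 1, 6 and 12 months are adjusted in the same way.

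The background section on risk factors for *S. aureus* SSTI states that "SSTI in a household contact was associated with increased risk of SSTI in the index patient". It also reports a relationship between *S. aureus* "household CP and a history of SSTI in household contacts in the year prior", and an association of high household MRSA colonization pressure (CP) with persistent MRSA colonization in the child. Potential limitations says that the decision to give antibiotics rests with the treating physician.

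**The concern.** A 2x2 chi-squared test and a Cochran-Armitage test, as named, take no covariates. If children from heavily exposed households are both more often colonized and more often reinfected, a crude association can appear when colonization itself does nothing. If prescribing happens to differ between colonized and non-colonized children, and antibiotics reduce recurrence, the crude association can also be weakened, reversed or inflated.

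The background presents MRSA colonization as conferring risk for SSTI, and the conclusion says that the data are meant to support a funding application. A positive result from either test is therefore likely to be read as evidence on a risk factor, which a crude pooled test cannot provide.

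**Working it through.** The plan gives no effect size or power for these two tests, so there is no figure of its own to reproduce. Its one power statement (Sample size) concerns the antibiotic comparison.

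**1. Household SSTI, with no true effect of colonization**

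From the documents: odds ratio (OR) of 2.9 for SSTI in the child when a household member had a skin infection in the year before enrollment (Figure 1, univariate). It comes from a general pediatric cohort and is assumed to carry over to children who already have an abscess, and to hold within colonization groups.

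Assumed, because the documents give no figure: 40% of children have the factor; 40% of the others are colonized; SSTI risk without the factor is 20%; the factor-colonization OR is 2, 3 or 4.

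SSTI risk with the factor: odds 0.25 x 2.9 = 0.725, so risk 0.725/1.725 = 0.420.

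For a factor-colonization OR of 3:

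- Colonized among those with the factor: odds (0.4/0.6) x 3 = 2, so 0.667.
- Factor among colonized: 0.4 x 0.667 / (0.4 x 0.667 + 0.6 x 0.4) = 0.526.
- Factor among non-colonized: 0.4 x 0.333 / (0.4 x 0.333 + 0.6 x 0.6) = 0.270.
- SSTI risk, colonized: 0.20 + 0.220 x 0.526 = 0.316.
- SSTI risk, non-colonized: 0.20 + 0.220 x 0.270 = 0.260.
- Crude OR: (0.316/0.684) / (0.260/0.740) = 1.32.

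The same steps give 1.19 for a factor-colonization OR of 2 and 1.41 for 4.

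A second set of assumptions (half the children colonized, 35% SSTI overall, factor prevalence in colonized v non-colonized from 40% v 30% up to 60% v 20%) gives 1.11 to 1.53.

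**2. Pooling over antibiotic treatment**

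Inputs: 50% recurrence untreated and 20% treated, from Sample size. The 20% is the upper end of the incidence that the plan says it could detect; it is not a prediction. The prescribing splits are assumed.

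Risk in a group = (share treated) x 0.20 + (share untreated) x 0.50. With no colonization effect:

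| Treated: colonized v non-colonized | SSTI risk | Crude OR |
|---|---|---|
| 50% v 50% | 0.35 v 0.35 | 1.00 |
| 60% v 50% | 0.32 v 0.35 | 0.87 |
| 60% v 40% | 0.32 v 0.38 | 0.77 |
| 40% v 60% | 0.38 v 0.32 | 1.30 |

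With a true conditional OR of 2, risks in colonized children become 0.667 untreated and 0.333 treated:

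- 50% v 50% treated: 0.50 v 0.35, crude OR 1.86. This is mild attenuation from pooling alone.
- 60% v 40% treated: 0.467 v 0.38, crude OR 1.43.

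**3. Bias beside noise**

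Take the 1.32 case with 25 colonized and 25 non-colonized children (an assumed split).

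- SE of log OR = sqrt[1/(25 x 0.316) + 1/(25 x 0.684) + 1/(25 x 0.260) + 1/(25 x 0.740)] = 0.63.
- The 95% interval is about 0.39 to 4.5.
- The bias is ln(1.32)/0.63 = 0.44 SE, which raises the upper-tail false positive rate from 2.5% to about 6%.

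**4. How much adjustment the data can carry**

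With 25 treated and 25 untreated children (assumed), expected recurrences are 25 x 0.50 + 25 x 0.20 = 17.5, or 25 x 0.50 + 25 x 0.125 = 15.6 at a 75% reduction.

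- Colonization plus antibiotic group: about 8 to 9 events per parameter.
- Adding household SSTI: about 5 to 6.
- Colonization plus three covariates: about 4.

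By 1 month there may be fewer events.

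**The case against.** The strongest reply is that both items ask descriptive questions: whether an association exists, and whether colonized children have more SSTIs. A crude test answers those questions. This stands, and it rules out the stronger inference that the results cannot be interpreted at all.

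Three other strong readings are tempting, and the documents do not support them.

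- *The plan contradicts itself.* Potential limitations says "Adjusting for possible confounding factors and covariates will be made", and a reader might take this as a promise that the two tests break. The sentence directly follows the remark on physicians' choice of antibiotics, so it concerns the antibiotic comparison, where the Specific Aim 2 models do adjust.
- *Prior SSTI is a documented confounder.* Figure 1 gives it an OR of 4.2 for SSTI, but the documents nowhere link it to colonization.
- *Antibiotics mask a colonization effect.* That needs prescribing to differ by colonization status, which is not documented. The swabs are shipped to an outside research laboratory and cultured there, and nothing shows that the result reached the prescriber. Any difference would have to arise indirectly.

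It is also fair that the household path is thin: the cited link is to persistent MRSA colonization, not to baseline *S. aureus* colonization, and it comes without a figure. With 50 children, imprecision outweighs the bias. These points lower the severity. They do not make the crude tests able to separate colonization from household exposure or treatment.

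**Conclusion.** The point holds as a limit on interpretation. Both tests are sound as descriptive associations. Neither can support colonization as an independent risk factor, because a plausible confounding path through household SSTI is set out in the plan's own background and treatment is not randomized.

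Household SSTI could move a null to a crude OR of about 1.2 to 1.4, given the assumed prevalences and a factor-colonization OR of 2 to 4. The antibiotic effect is conditional: none under a null if prescribing is equal, and about 0.77 or 1.30 if it differs by 20 percentage points in one direction or the other. The severity is minor, since both analyses are secondary in a pilot aimed at feasibility and preliminary data.

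**What to change.** Keep both crude tests, including the assessment of SSTI over the year in Specific Aim 2, and label them unadjusted. Replacing them outright would discard a valid description and the stated interest in trend.

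Beside each, add one of the following:

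- a Mantel-Haenszel analysis of SSTI by baseline colonization, stratified by antibiotic group; or
- a Firth-penalized or exact logistic model of SSTI on baseline colonization with antibiotic group as covariate.

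In the model, add household SSTI before enrollment if the enrollment questionnaire captures it and events allow. Data Collection describes that questionnaire only as covering risk factors and names household SSTI only at the 1-month visit and the phone calls, so this must be checked. Household SSTI reported after enrollment is not a substitute, because it may itself follow from the child's colonization or infection.

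State that only the added analyses bear on whether colonization matters apart from treatment and household exposure.

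Cost: SAP wording and a little analysis time. Antibiotic use is already recorded at enrollment. The interval will be slightly wider, and only one or two covariates can be carried with 50 children.

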### Specific Aim 2:

#### *Primary outcome:*

To measure incidence of SA recurrent skin and soft tissue infections at 3 months in patients who did or did not receive systemic antibiotic therapy. A binary logistic regression will be performed to see if antibiotic therapy is associated with SSTI at 3 months after adjusting for covariates.

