### **Management of CA-S. aureus abscesses**

It is controversial whether abscesses requiring incision and drainage also require antibiotics [28]. The frequency of antibiotic prescription in *S. aureus* SSTI is still common as described in the literature [29]. Creech et al surveyed over 100 Pediatric Infectious Diseases Consultants and found that all of them (N=197) prescribed antibiotics; no provider reported using incision and drainage alone without antibiotic therapy [30]. Mc Neil et al reported an almost 95% rate of antibiotic prescription among children with *S. aureus* SSTI at Texas Children's Hospital [31].

In a study done by Ruhe et al, patients with SSTIs caused by MRSA benefited from antibiotic treatment. Patients with CA-MRSA SSTI who received antibiotics in addition to incision and drainage had a greater treatment success rate (infection cure) than those managed with incision and drainage alone (95% versus 87%,  $P = .001$ ) [32]. In a randomized trial by Duong et al, treatment failure rates for CA-MRSA skin abscesses were similar after incision and drainage between patients who received antibiotics and those given a placebo. However, at 10-day follow-up, new lesions formed in 26.4% of cases in the placebo group and only 12.9% of cases in the antibiotic group [12]. Schmitz et al showed a similar incidence of treatment failure in adult patients with uncomplicated abscesses receiving trimethoprim-sulfamethoxazole versus placebo (17% vs 26%,  $P = .12$ ); but at 30-day follow-up the incidence of new lesions was lower in the antibiotic group compared to the placebo group (9% vs 28%,  $P = .02$ ) [33].

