**Figure 1**  
Significant Risk Factors for Development of SSTI during a 12- Month Longitudinal Study, Univariate Analysis

| Risk Factor   | OR  | 95% CI     |
|---|-----|------------|
| MRSA nasal colonization   | 4.6 | 1.8 – 11.9 |
| Skin infection in year prior to enrollment                              | 4.2 | 1.8 – 9.7  |
| Household member with skin infection in year prior to enrollment        | 2.9 | 1.2 – 6.8  |
| Interval skin infection in a household member during one-year follow up | 6.4 | 3.4 – 12.2 |
| African-American race   | 3.1 | 1.5 – 6.4  |
| Crowded home (>2 people/bedroom)  | 4.4 | 1.1 – 18.2 |

Inclusion criteria: (1) Children 6 months to 18 years presenting with a skin abscess. (2) Positive MRSA or MSSA culture from previous or current abscess

Exclusion criteria: (1) Immunodeficiency; (2) Hospitalization within the prior 14 days; (3) Use of mupirocin, chlorhexidine or bleach water baths in the last month; (4) Systemic antibacterial therapy with anti-staphylococcal activity within the prior 14 days.

Assent will be obtained from children greater than 7 years of age. Informed consent will be obtained from the patient's parent or legal guardian. The study protocol was approved by the Southern Illinois University (SIU) Institutional Review Board (IRB). Risks for participating in the study are minimal; the only intervention that will be done is collection of body surfaces swabs.

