Data Collection: At study enrollment, a detailed questionnaire will be administered to identify risk factors for *S. aureus* colonization, infection, and transmission. Clinical data will be collected as well to track clinical signs at the time of presentation (vital signs, body site of infection, size of abscess, presence of systemic symptoms, type of incision and drainage, antibiotic use, type of packing applied). In addition, colonization swabs from the nose, axilla, inguinal folds and wound isolate will be collected and transported to [name] laboratory at Washington University. Longitudinal study visits will be conducted at the SIU Pediatric Infectious Disease Clinic one month following enrollment for research purposes only by PI or by the research coordinator. At this visit, a follow-up questionnaire will be administered inquiring about new, recurrent, or relapsed infection. Colonization swabs will be obtained and transported to [name] laboratory. Also history of any household members with any recent SSTI will be asked. Follow-up phone calls will be administered at 3, 6 and 12 months after enrollment to ask about recurrent infections. If an interval infection did occur, we will collect data regarding whether the individual sought medical care (and if so, the location where medical care was sought), the date of infection, the body site of infection, the bacteria causing infection, if known, whether the individual required a drainage procedure, surgery, or hospitalization, and whether the participant received antibiotics, oral or intravenous. If the patient sought medical care, records from the hospital and/or provider's office will be obtained for verification. Again, question about any household member having an SSTI will be made. Throughout the longitudinal study, we will ask participants to contact us if they develop a SSTI. The participant will be directed to seek medical treatment from their primary healthcare provider.

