Microbiology: Colonization swabs will be obtained at enrollment and at the 1 month follow-up visit by the PI or the research coordinator from the nose, axilla and inguinal folds. Four swabs will be used for each participant (1 each for both nostrils, both axillae, and both sides of the groin and the abscess site). Specimens will be collected with Copan E-swab™ Collection and Transport System to evaluate *S. aureus* colonization. This is a liquid-based multipurpose collection and transport system that maintains viability of aerobic, anaerobic and fastidious bacteria for 48 hours at room and refrigerator temperature. The research coordinator and I have successfully completed training for Shipping Infectious Materials and Biological Substances with SIU School of Medicine. Specimens will be shipped to Washington University in St. Louis, to the laboratory of [name] for microbiologic studies. If wound isolates from initial infection and a recurrence are available, they will be requested at the microbiology laboratory at SJH or MMC. After arrival, specimens will be incubated overnight in tryptic soy broth with 6.5% NaCl at 35°C. A sample of the broth will be plated to mannitol salt agar and incubated for 24-48 hours. Following confirmatory testing for *S. aureus* [37], susceptibility testing for cefoxitin (a surrogate for methicillin resistance) and 9 other antibiotics will be determined by Kirby-Bauer disk diffusion, in accordance with published guidelines [37]. Inducible clindamycin resistance will be tested [38]. All isolates will be stored in glycerol at -20°C.

Sample size: This is a pilot study to determine the feasibility of recruiting patients as described, having them return for 1 follow-up visit, and collaborating with Washington University for future

investigations. Our goal is to get preliminary data. According to available billing records (ICD-9 codes), since 2010, there has been in average 130 pediatric visits per month at SJH, MMC ED and Express Cares secondary to SSTI. Our goal is to recruit 50 patients in 12 months, which means that we will need about a 30% success rate for recruitment (**Figure 3**). A sample size estimate was performed to evaluate the power in the study. Considering an incidence of recurrent SSTI of 50% in patients who did not receive antibiotic therapy, a 60-75% percent reduction of recurrent SSTI (12-20% incidence) can be shown with 50-80% power.

[figure not shown]

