### Data Analysis Plan

Data on *S. aureus* identification will be collected from Washington University School of Medicine and recorded, along with questionnaire and clinical variables, on a data collection form by the principal investigator and research coordinator and then transferred to an excel spreadsheet for statistical analysis. Statistical Package for the Social Sciences (SPSS), version 20, will be used for data analysis.

Descriptive Statistics will be computed for all study variables. Continuous variables will be described with measures of central tendency (mean, median) and dispersion (range, standard deviation). Categorical variables will be summarized as frequencies and percentages.

We will calculate the frequencies/percentages for patient demographics, clinical characteristics, baseline questionnaire, follow-up questionnaires, and *S. aureus* colonization (nose, axilla, and inguinal folds) for each group: 1) Systemic antibiotic therapy 2) No systemic antibiotic therapy. Characteristics will be compared using independent t-tests for continuous variables and Chi-squared tests of independence for categorical variables. Significance will be assumed when  $p < 0.05$  or the 95% confidence interval.

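### Aim 2's adjusted logistic regressions state no small-sample method; with 50 patients, ordinary maximum likelihood would overstate a true antibiotic effect, and Firth penalisation is a cheap improvement

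*Combined protocol and SAP*

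**What the plan says.** Specific Aim 2 takes recurrent SSTI at 3 months as its primary outcome: "A binary logistic regression will be performed to see if antibiotic therapy is associated with SSTI at 3 months after adjusting for covariates". For 1, 6 and 12 months the secondary outcomes add: "Separate logistic regressions will be performed (at each time point) to see if antibiotic therapy is associated with SSTI after adjusting for covariates". That makes four adjusted models in a planned 50 patients.

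On estimation, the Data Analysis Plan says only: "Statistical Package for the Social Sciences (SPSS), version 20, will be used for data analysis". No penalised, exact or other small-sample method appears anywhere.

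On covariates, Potential limitations promises adjustment for confounders but gives no list, number or selection rule. Figure 1 shows six risk factors from an earlier study, for example "Household member with skin infection in year prior to enrollment". Under Data Collection, at enrolment "a detailed questionnaire will be administered to identify risk factors for" *S. aureus* colonization, infection and transmission. Neither is designated as the adjustment set.

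The sample-size paragraph is the only source for event rates: "Considering an incidence of recurrent SSTI of 50% in patients who did not receive antibiotic therapy", against 12-20% with antibiotics. It attaches no time point to these rates. No split between the groups is given, because treatment is not randomised: "A source of bias that we will have is the variability in the treating" physician's decision. The background cites an "almost 95% rate of antibiotic prescription among children with" these infections at one children's hospital elsewhere, so an uneven split is possible.

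**The concern.** Logistic regression fitted by ordinary ML is biased away from the null when events are few relative to the number of coefficients. The bias shrinks as the sample grows, but 50 patients is small. Treatment is chosen by the physician, so adjustment cannot simply be dropped, and each added covariate makes the bias worse. In some data sets ML has no finite estimate at all.

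At stake is the size of the antibiotic effect that Aim 2 reports. The Conclusion says that the data will support applications for external funding. An inflated odds ratio carried into the next study's sample-size calculation would make that study too small.

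**Working it through.** **Inputs from the document.** N = 50; recurrence 50% without and 12-20% with antibiotics (sample-size paragraph); significance at p < 0.05 (Data Analysis Plan; two-sided assumed). **Assumed, because the document does not say:** the split; 1, 3 or 6 binary covariates, each with prevalence 0.4 and odds ratio 2; the stated rates applying at the time point analysed.

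**The plan's own power figure.** The stated 60-75% reduction gives 50% × 0.40 = 20% and 50% × 0.25 = 12.5%. At 25:25, Fisher's exact test has 51% power against 20% and 76-77% against 12.5-12%. The pooled normal formula gives 61% and 84-85%. The stated 50-80% is therefore roughly consistent with its inputs. It describes an unadjusted comparison and says nothing about bias in an adjusted odds ratio.

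**Expected events**, as untreated × 0.50 + treated × (0.12 to 0.20):

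- 25:25 (treated:untreated): 12.5 + 3.0 to 5.0 = 15.5 to 17.5
- 40:10: 5 + 4.8 to 8.0 = 9.8 to 13.0
- 45:5: 2.5 + 5.4 to 9.0 = 7.9 to 11.5
- 10:40: 20 + 1.2 to 2.0 = 21.2 to 22.0

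**Methods compared.** ML maximises l(β). Firth maximises l(β) + ½ log|I(β)|, where I(β) is the information matrix; this removes the leading small-sample bias and keeps estimates finite. For 50% versus 20%, the true conditional log odds ratio is ln[(0.20/0.80)/(0.50/0.50)] = ln 0.25 = -1.386.

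**Simulation, 50% versus 20%, 4,000 trials per cell.** Non-finite ML fits are kept in the medians. Root mean squared error (RMSE) uses only trials with a finite ML fit, which favours ML. Percentages come from the rounded medians shown.

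| Split | Covariates | Median ML (overstatement) | Median Firth | RMSE ML / Firth |
|---|---|---|---|---|
| 25:25 | 1 | -1.44 (4%) | -1.33 | 0.74 / 0.65 |
| 25:25 | 3 | -1.56 (13%) | -1.37 | 0.88 / 0.70 |
| 25:25 | 6 | -1.69 (22%) | -1.35 | 1.14 / 0.76 |
| 40:10 | 1 | -1.47 (6%) | -1.37 | 0.89 / 0.76 |
| 40:10 | 3 | -1.55 (12%) | -1.36 | 1.01 / 0.81 |
| 40:10 | 6 | -1.74 (26%) | -1.38 | 1.34 / 0.89 |
| 45:5 | 1 | -1.46 (5%) | -1.37 | 1.01 / 0.81 |
| 45:5 | 3 | -1.55 (12%) | -1.36 | 1.18 / 0.90 |
| 45:5 | 6 | -1.75 (26%) | -1.38 | 1.58 / 1.03 |
| 10:40 | 1 | -1.52 (10%) | -1.31 | 0.80 / 0.70 |
| 10:40 | 3 | -1.59 (15%) | -1.33 | 0.92 / 0.75 |
| 10:40 | 6 | -1.74 (26%) | -1.33 | 1.21 / 0.86 |

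In this table Firth's RMSE is lower throughout, by 12% (0.65/0.74) to 35% (1.03/1.58). ML had no finite estimate in under 1% of trials at 25:25, and in up to about 10% at 45:5 and 10:40.

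**At 12% treated risk** the bias is somewhat larger. At 25:25 and 40:10, one set of runs gave 6-8%, 11-17% and 29-36% with one, three and six covariates; another gave 24-28% with six. At 10:40 with one covariate, over 20% of ML fits were not finite. That is the one cell where Firth's RMSE, on the trials ML could fit, was not lower (ML 0.73, Firth 0.76). Firth was about 7-9% too small at that split.

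**Checks on the cause.** With no true effect, the median ML log odds ratio was -0.01 to 0.03. At 500 patients with four covariates, the mean ML estimate was only 1% too large.

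**The case against.** The strongest objection is that the larger figures need six covariates, which the document never promises. This stands. With one to three covariates, the shift at 50% versus 20% is 0.05 to 0.20 on the log odds ratio scale (1.44 - 1.39 to 1.59 - 1.39). The unadjusted standard error at 25:25 is √(1/12.5 + 1/12.5 + 1/5 + 1/20) = 0.64, so bias is minor beside noise. However, Firth reduces the noise as well.

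A second objection is that a short covariate list would remove most of the bias without changing the estimator. That can cost more than it saves. In a simulation with six true confounders, Firth with only three of them gave -0.98 at 25:25 and -0.92 at 40:10, about 30-34% too small; with all six it was within 3%. Part of that gap reflects non-collapsibility of the odds ratio and not confounding alone, but brevity is clearly no substitute for choosing confounders.

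Results also depend on the assumed covariate strength. With Figure 1's five baseline factors at their reported odds ratios (prevalence 0.3 assumed), ML was about 17% too large and Firth 5-6% too small. That setting implies a treated risk of about 27%, outside the planned 12-20%, so it is only a sensitivity check.

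A reader might infer that the planned tests would produce spurious positive findings. The calculations do not support this: under no effect there is no material bias, and Wald type I error was 0.4-5.7%. Nor does an unnamed covariate list amount to a quantified error; it is missing detail, and the simulations fix the covariates in advance.

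**Conclusion.** The point holds as an efficiency and accuracy improvement for Aim 2. If an effect of the planned size exists, ordinary ML would overstate the log odds ratio by a median of roughly 5-12% with one covariate, 11-17% with three and 22-35% with six. Firth's median is within about 8% of the truth, and within about 4% when half or more are treated. These figures rest on ML being the intended estimator, on the assumed covariates and splits, and on the 50% versus 12-20% rates applying at the time point analysed. The document does not fix any of these.

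It would be tempting to call Aim 2 invalid or the study's main result compromised. The document does not support that: it describes a pilot seeking preliminary data, and Potential limitations names colonization as the primary outcome. Residual confounding from physician-chosen treatment is a separate matter that Firth does not cure.

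**What to change.** Fit all four Aim 2 models by Firth penalised-likelihood logistic regression, with profile penalised-likelihood intervals and tests. Before analysis, choose the adjustment variables from baseline data already collected (for example abscess size, systemic symptoms, skin infection in the prior year) because they may drive both the antibiotic decision and recurrence. Do not drop a confounder merely to shorten the list. Report the unadjusted risk in each group with an exact interval; for example, 5 of 25 gives 7-41% and 5 of 10 gives 19-81%, which shows readers how little the data can settle.

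The cost is plan wording and possibly software other than SPSS 20. Estimates will be somewhat smaller than under ML. At 25:25 and 40:10, power of the Firth profile test was within 1 point of the Wald ML test with one or three covariates and 1-3 points lower with six. Its type I error was 4.1-5.3%, against 4.1-7.7% for the ordinary likelihood-ratio test. No extra patients or data are needed.
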